If a participant expresses suicidal ideation during treatment or at subsequent assessments, assessors will initiate a structured suicide risk assessment in accordance with routines at the clinic. If there is an urgent need for psychiatric care, a trial psychiatrist will contact participants to schedule an appointment as soon as possible. Serious adverse events (e.g., urgent psychiatric care or discontinued treatment due to a worsening of psychiatric symptoms) will be described in detail on a case-by-case basis.

Statistical analysis

All analysis scripts have been uploaded to a public repository with the analysis strategies described in detail using simulated data (<https://osf.io/w5bfp/>).

Primary outcome

Y-BOCS

The primary non-inferiority hypothesis on the clinician-rated Y-BOCS will be evaluated using ANCOVA of group differences at post-treatment with pre-treatment score as covariate. It will be based on participants that have received at least 50% of the treatment (i.e., attended at least 8 sessions of individual CBT or 1.5 days of B4DT) and completed the post treatment assessment 14 weeks after treatment start. This per protocol approach is chosen to avoid potential problems related to study design that can bias the results towards the alternative hypothesis of non-inferiority (the opposite is true in superiority trials). No data imputation will be conducted at this stage. A 95% confidence interval will be used to model the gold standard CBT-B4DT effect. Non-inferiority will be considered supported if the upper bound is less than 4 (the non-inferiority margin) and superiority will be considered supported if the upper bound is less than 0. This testing procedure has the Type I error rate controlled at the 2.5% level for both comparisons.

For sensitivity assessment, the same ANCOVA model will be used again but with an intention to treat approach. Missing data will then be estimated using maximum likelihood after which the models are refitted. The aim of these steps is to address the potential influence of non-random missing data in the primary per protocol analysis.

Non-inferiority margin

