Although there are no strict guidelines regarding the selection of non-inferiority margins, half the placebo-controlled effect of gold-standard treatment is often recommended as adequate [23]. The proposed non-inferiority margin of 4 is smaller than half of the 10-point effect for ERP on the Y-BOCS [4], and would therefore be a stringent non-inferiority margin. Moreover, a non-inferiority margin of 4 points gives similar precision compared to previous non-inferiority trials for OCD in adults that have used 5 points [19] or 3 points [20], and a previous non-inferiority trial in pediatric OCD that used a margin of 4 points [30]. From a clinical point of view, a 4-point margin on the Y-BOCS is considered a small but observable difference in OCD symptoms.

Secondary outcomes

While this study was designed to have high power to assess the primary hypothesis, we do not have sufficient power to robustly compare the secondary outcomes between the treatment arms without inflating the false positive rate. This means that the results from these analyses should be interpreted with caution. On secondary outcomes, our approach will be to compute 95% confidence intervals of group differences without comparing the bounds to any predefined margin. Because the non-inferiority testing procedure will not apply, the secondary outcomes will be analyzed using an intent to treat approach including all randomized participants.

Moreover, we do not plan to collect data continuously throughout the treatments since our focus is on the pre-post comparisons. This decreases the usefulness of statistical methods that make imputations based on past observations. Therefore, unless the proportion of missing data exceeds 10%, no data imputation methods will be used as default (unless stated otherwise). However, if the proportion of missing data exceeds 10%, we will perform maximum likelihood imputations based on demographics and the scores from the pre-treatment assessment to complement the complete case analyses. The implications of these analyses on the reliability of the results will be discussed.

Time to response

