(pretreatment) or the past 14 weeks (post-treatment and follow-up), and costs will be extrapolated to cover the entire period between assessments when needed. Costs from third party payer (including only intervention costs), healthcare, and societal perspectives will be analyzed in relation to clinical efficacy (responder status; cost-effectiveness analysis) and quality-adjusted life-years on the AQoL-6D (QALYs; cost utility analysis). Additional cost-effectiveness analyses will use remitter status as outcome. The economic analysis will be conducted using multiple imputation of missing values. Cost data and QALYs will be analyzed using generalized linear models (GLM) to allow for the consideration of other distributions and functional forms to fit the cost and outcome data [24]. Total costs will be analyzed while controlling for baseline costs. Total QALYs will be analyzed while controlling for baseline AQoL-6D utility values [25].

A micro costing framework will be used to estimate the cost of delivering the interventions prospectively. Intervention costs will include the therapists' time to deliver sessions, as well as any training needed. Healthcare resource use will be costed using national pricelists, and medication costs using market prices, and estimated by multiplying frequencies of resources used by unit costs. Unit costs for resources related to social support and assistance will be sourced from published sources or based on authors' own estimates. Productivity losses will be estimated using the human capital approach [26]. Productivity losses due to absenteeism from paid work will be the product of the number of days off from work by individuals due to mental illness by the average hourly salary rate in Sweden [27] including social fees. Losses due to absenteeism from unpaid work will be the product of the number of days not performing unpaid work by the estimated hourly cost of leisure time [28]. Productivity losses related to reduced efficiency at work will be estimated in the same fashion as productivity losses due to absenteeism, but additionally multiplied by a weighed score representing how the illness impacted the participants' productivity [29].

Additional outcomes used for quality assessment

Therapist competence and adherence

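### The intention-to-treat sensitivity analysis, and the rule for secondary outcomes with more than 10% missing, fill in values by maximum likelihood without carrying imputation uncertainty into the standard error

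*Combined protocol and SAP*

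**What the plan says.** The relevant text is in three places under Statistical analysis.

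- **Primary outcome, Y-BOCS.** The primary test is a per-protocol ANCOVA on completers, and "No data imputation will be conducted at this stage". The upper bound of a 95% interval is compared with 4 and then with 0, and the plan adds: "This testing procedure has the Type I error rate controlled at the 2.5% level for both comparisons". The next paragraph introduces the robustness check: "For sensitivity assessment, the same ANCOVA model will be used again but with an intention to treat approach". It continues: "Missing data will then be estimated using maximum likelihood after which the models are refitted".
- **Secondary outcomes.** These are analysed on all randomized participants. The approach is to "compute 95% confidence intervals of group differences without comparing the bounds to any predefined margin". If more than 10% of data are missing, "we will perform maximum likelihood imputations based on demographics and the scores from the pre-treatment assessment to complement the complete case analyses".
- **Cost effectiveness.** "The economic analysis will be conducted using multiple imputation of missing values".

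Neither of the first two sections says how many fills are made, whether residual variation is added, or how the interval allows for the values being estimated. The plan says that all scripts are in a public repository; they were not among the documents reviewed.

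**The concern.** The sensitivity sentence describes two steps: estimate the missing data, then refit the model. Direct (full-information) likelihood has no such steps, because it fits the model to the observed data and fills nothing in. The secondary-outcome text speaks of imputations, which also points to filling. The economic section names multiple imputation, so the authors use that term when they intend it. The plain reading is therefore a single fill and an ordinary refit.

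Values filled from a regression lie exactly on the fitted line. The refit counts them as extra patients with no residual scatter, so the residual variance and the standard error both come out too small. The more data are missing, the shorter the interval becomes, when it should become longer.

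This matters because the primary analysis is restricted to completers with at least half the treatment. The intention-to-treat analysis is the only planned primary-outcome analysis on everyone randomized, and its stated purpose is to deal with missing data. An interval that is too short makes it agree with a non-inferiority or superiority claim too readily.

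**Working it through.** **Inputs from the plan.** Sample size calculation: 60 per arm, baseline 22.6 (SD 3.78), post-treatment CBT 12.9 (SD 4.07), 10% missing, more than 95% power at no true difference. Y-BOCS section: margin 4, two-sided 95% interval. Response and remission cut-offs: a 35% reduction, and a score of 12 or less.

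**Assumptions.** Baseline-post correlation r = 0.3 (not given in the plan; 0 and 0.4 give the same picture), equal SDs, outcomes missing completely at random, arm included in the fill model, difference taken as B4DT minus CBT so that positive values favour CBT.

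**1. The plan's power figure.** With 54 per arm (60 × 0.9) and r = 0, SE = 4.07 × √(2/54) = 0.783. Power = Φ(4/0.783 − 1.96) = 99.92%. With r = 0.3 it is 99.97%. The stated figure of more than 95% is reproduced.

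**2. Why the SE shrinks.** Let n be the number observed, N = 120, m = 1 − n/N, and σ = 4.07 × √(1 − 0.3²) = 3.88.
- Correct SE: σ × √(2/(n/2)).
- SE after fill and refit: the residual sum of squares is unchanged but is divided by N − 3 = 117 instead of n − 3, and the arm size is taken as 60. This gives σ × √((n − 3)/117) × √(2/60).
- The ratio is close to n/N = 1 − m, so the one-sided error at the margin is about Φ(−1.96 × (1 − m)).

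At 10% missing (n = 108): correct SE 3.88 × √(2/54) = 0.747; filled SE 3.88 × √(105/117) × √(2/60) = 0.672; ratio 0.90. At 20% (n = 96): 0.793 and 0.632; ratio 0.80.

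**3. Simulation** (20,000 trials per row, true difference 4, r = 0.3):

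| Missing | Reported SE | True SD of estimate | Coverage of 95% CI | One-sided error, filled | Φ(−1.96(1 − m)) | One-sided error, complete cases |
|---|---|---|---|---|---|---|
| 10% | 0.673 | 0.754 | 92.2% | 4.0% | 3.9% | 2.6% |
| 20% | 0.633 | 0.799 | 88.1% | 5.9% | 5.8% | 2.4% |
| 30% | 0.590 | 0.851 | 82.8% | 8.4% | 8.5% | 2.5% |

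Repeat runs with r = 0 or 0.4 gave 3.8–4.2%, 5.7–6.3% and 8.5–9.0%. Adding one random residual to each filled value does not cure the problem (3.6%, 5.0%, 6.7%). Multiple imputation with Rubin's rules at 20% missing gave 2.5% error and 95.6% coverage (4,000 trials). The filled and complete-case analyses had the same mean estimate (4.004 at 10% missing) and the same true SD, so in this setting the fill adds no information and only shortens the interval.

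**4. Where it changes the answer.** The half-width at 10% missing is 1.96 × 0.673 = 1.32 instead of 1.96 × 0.754 = 1.48. The two disagree at the margin only if the estimate lies between 4 − 1.48 = 2.52 and 4 − 1.32 = 2.68. At 20% missing the half-widths are 1.24 and 1.57, and the window is 2.43 to 2.76. A window of the same width lies just below 0 for superiority, from −1.48 to −1.32 and from −1.57 to −1.24.

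**5. Response and remission, if status is derived from a predicted Y-BOCS.** Cut-offs on the Y-BOCS only, baseline restricted to 16 or more as at entry, r from 0 to 0.5:

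| Arm mean | Outcome | Filled patients | True |
|---|---|---|---|
| 12.9 (plan, CBT) | response | 80–100% | 67–70% |
| 12.9 (plan, CBT) | remission | 0–30% | 40–41% |
| 16.9 (at the margin) | response | 0–19% | 27–33% |
| 11 (assumed) | remission | 68–100% | 58–60% |

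For example, at r = 0 every filled CBT patient scores 12.9 and none is in remission, while Φ((12 − 12.9)/4.07) = 41% truly are. At mean 11 every filled patient is in remission, against Φ((12 − 11)/4.07) = 60%.

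**The case against.** **The wording does not prove a single fill.** The plan does not say that each value is filled once or then treated as observed. Its sentence could be loose shorthand for direct likelihood, which gives valid standard errors, and the scripts would settle this. That stands, and it makes the size conditional. It does not remove the point: the text describes filling and refitting, gives no variance method, and would need rewriting even if the code is sound.

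**The 2.5% statement.** A reader might infer that the trial's error rate is exceeded. The documents do not support that. The statement describes the per-protocol test, which uses no imputation, and no error rate is claimed for the sensitivity analysis. In a check on the same simulated patients, the proportion of trials in which both the filled and the unimputed test rejected equalled the unimputed test's own rate. If the unimputed test decides, the fill adds no false claims.

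**Secondary outcomes.** These are exploratory, have no margin, and the imputed results only supplement complete-case ones. An error-rate breach has no meaning there. Intervals that are too short still do.

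**Direction of the response and remission shift.** It is tempting to say that response is always pushed up and remission down. That is true at the plan's CBT mean of 12.9, but it reverses for response at 16.9 and for remission at 11. The plan also does not say that status would be derived from predicted scores, and both definitions need a CGI rating as well.

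**Practical effect.** If the treatments are truly equal, power exceeds 99.9% with or without the fill, so the non-inferiority conclusion would rarely change.

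**Conclusion.** The point holds for the plan as worded. Carried out literally, the intention-to-treat standard error is about 10% too small at 10% missing and about 20% too small at 20%. The plan's non-inferiority rule applied to that interval would have a one-sided error of about 4% and 6% instead of 2.5%. These figures assume data missing completely at random, equal SDs, arm in the fill model and a pre-post correlation between 0 and 0.4. They are conditional on the scripts doing what the text says.

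The primary per-protocol test and its 2.5% statement are not affected. The harm is false reassurance from the supporting analysis, mainly when its upper bound lies near 4 or 0. For the exploratory secondary outcomes the defect is narrow intervals and, if status comes from predicted scores, distorted imputed response and remission rates, in a direction set by where the arm mean lies relative to the cut-off. The change should be made, but the primary conclusion does not depend on it.

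**What to change.** Replace the sensitivity sentence in the Y-BOCS section with one of:

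- (a) direct (full-information) likelihood on the observed data, with no values filled in and the interval taken from that fit; or
- (b) multiple imputation with residual variation, arm in the imputation model, and Rubin's rules.

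Make the same change in the more-than-10% rule for secondary outcomes. If (b) is used there, add arm to the imputation variables, which now list only demographics and pre-treatment scores. For response and remission, impute Y-BOCS and CGI and derive status within each imputed data set. Check the posted scripts against the new text.

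The cost is two sentences and a few lines of code; multiple imputation is already planned for the economic analysis. Compared with the single-fill interval, the corrected one is wider by 1/(1 − m) − 1: about 11% at 10% missing, 25% at 20% and 43% at 30%. That is its correct width.

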Obsessive-compulsive disorder (OCD) is a disabling psychiatric disorder characterized by recurrent uncontrollable and unwanted thoughts (obsessions), and repetitive behaviors in response to those obsessions (compulsions). The lifetime prevalence of OCD is 2-3% [1], and the time-consuming symptoms often interfere with all aspects of daily life. Moreover, population-based studies have shown that OCD is associated with academic underachievement across the lifespan [2] and with substantial labor market marginalization, including higher risk of receiving disability pension, being on long-term sickness absence, and long-term unemployment [3].

One of the recommended first-line treatments for OCD is individual cognitive behavioral therapy (CBT) that includes exposure and response prevention (ERP). In CBT, patients are exposed to situations that trigger obsessions while actively refraining from performing compulsions. Although it is an effective treatment with 65% of participants responding to treatment [4], CBT typically requires weekly sessions during at least 3 months [5]. This extensive time-frame requires significant effort and persistence from patients and increases the risk of dropout. Moreover, a substantial proportion of patients remain impaired even among those who complete the treatment.

In response to this, several condensed formats of CBT have been developed in various countries. Amongst them is the Bergen 4-Day Treatment (B4DT), developed in Norway. In this treatment, patients receive intensive CBT at the clinic for 4 consecutive days. B4DT has been shown to achieve response rates over 90% when delivered in regular care in several uncontrolled treatment trials, and one randomized controlled trial (RCT) that used waitlist and self-help as controls [6]. However, it has yet to be compared to the gold standard CBT.

In this non-inferiority RCT, we will test the efficacy of B4DT compared to gold standard CBT. If B4DT turns out to be non-inferior to traditional CBT, the range of evidence-based options will be broadened and patients may be able to achieve clinically meaningful improvements within a shorter period of time.

Research questions

The overall approach of this study is to directly compare the intensive Bergen 4-day treatment (B4DT) to gold-standard individual cognitive behavior therapy (CBT) for adults with OCD.

Primary outcome

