Therapists in both arms will be licensed clinical psychologists or psychologists under supervision employed at the two specialist OCD clinics. All sessions in both treatments will be audiotaped for the purpose of rating competence and adherence. Such ratings will be conducted on 20% of audiotaped sessions (randomly selected) by two independent psychologists not otherwise involved in the study specialized in B4DT, and two independent psychologists specialized in individual CBT treatment for OCD. Adherence to protocol in the B4DT arm will be checked using a treatment checklist, and therapist adherence in the individual CBT arm will be checked using the session checklist in the treatment manual. Therapist competence in both treatment arms will be rated using the Cognitive Therapist Scale-Revised (CTS-R) [22].

Sample size calculation

A power calculation has been conducted in order to determine the number of participants needed to test the primary hypothesis; that B4DT will be non-inferior compared to gold standard CBT at the pre-specified margin of 4 points on the Y-BOCS. Clinical outcome data from a recent randomized controlled trial (individual CBT) and regular clinical practice (B4DT) were obtained to simulate study data. The following parameters were used: A pre-treatment mean of 22.6 (SD = 3.78) for both arms, and a post-treatment mean of 12.9 (SD = 4.07) for the gold standard CBT arm. Statistical power was then assessed by simulating 10000 datasets assuming different true group differences. An ANCOVA was then conducted on each dataset to test for between-group differences at post-treatment accounting for pre-treatment scores. With 60 participants per arm, no difference in efficacy between the treatments, and 10% missing values,

this test has >95% power to demonstrate non-inferiority. Details on this calculation, including analysis code, is provided in the online pre-registration (<https://osf.io/w5bfp/>).

Measurements

Table 2 lists clinician-rated and self-rated assessments at the different time points.

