The primary outcome measure is the blind assessor-rated Y-BOCS, which will be administered at pre-treatment, at weeks 4 and 7 during treatment, 14 weeks after treatment start (primary endpoint), and at the 7- and 16-month follow-ups [21]. Blinded assessors will undergo training prior to conducting clinician-rated assessment and practice on videos of OCD case examples. In order to be allowed to conduct assessments for the project, the assessors will have to deviate no more than 1 point on single items, no more than 2 points on the obsessions subscale and the compulsions subscale and no more than 4 points on the Y-BOCS total score compared to expert raters at the two clinics. Inter-rater reliability on the Y-BOCS will be reported.

Secondary clinician-administered outcome measures are the Clinical Global Impression – Severity and Improvement (CGI-S, CGI-I), the Patient Exposure/Response Prevention Adherence Scale (PEAS), the Structured Clinical Interview for DSM-5 for OCD and related disorders (SCID-5) and the Mini International Neuropsychiatric Interview. SCID-5 and MINI will be administered at pre-treatment to confirm the OCD-diagnosis and assess comorbidities

Secondary self-rated outcome measures are the Obsessive-Compulsive Inventory-Revised (OCI-R), self-rated Y-BOCS, Montgomery-Åsberg Depression Rating Scale—Self-Rated (MADRS-S), Work and Social Adjustment Scale (WSAS), Assessing Quality of Life 6 Dimensions (AQoL-6D) (for economic evaluation), Credibility/Expectancy Questionnaire (CEQ), Working Alliance Inventory—Short Form Revised (WAI-SR), the TIC-P resource use questionnaire (for economic evaluation), and the Negative Effects Questionnaire (NEQ). Participants will also rate their treatment preference measured on a 7-point Likert-type scale (pre-treatment and post-treatment).

Table 2. Assessments of secondary outcomes at different time points

	Pre-treatment	Week 4	Week 7	Week 15 (primary end-point)	7-month follow-up	16-month follow-up
Clinician-rated instruments						
SCID-5 (OCD)	X					
MINI	X					
Y-BOCS	X	X	X	X	X	X

CGI-S	X	X	X	X	X	X
CGI-I		X	X	X	X	X
PEAS*		X	X	x		
Self-rated instruments						
YBOCS-SR	X			X	X	X
OCI-R	X			X	X	X
MADRS-S	X			X	X	X
WSAS	X			X	X	X
AQoL-6D	X			X	X	X
TIC-P	X			X	X	X
NEQ				X	X	X
Other adverse events		X	X	X	X	X
CEQ**		X				
WAI-SR**		X				
Treatment preference	X			X		

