To explore whether B4DT leads to a faster treatment response than individual CBT, the proportion of responders in the two treatments will be compared 4 weeks after treatment start. The 95% confidence intervals of the odds ratio of response will be calculated for this purpose. Because the B4DT-group will have received their full treatment dose at the point of assessment while the gold standard CBT-group will have received only about 25%, there are strong reasons to believe that, from this perspective, B4DT will lead to faster symptom relief. An identical analysis will be conducted at 7 weeks to evaluate whether there is a difference between the treatments when participants in the individual CBT group have received 50% of the treatment.

Rates of response and remission

The proportion of participants in response and remission will be compared 14 weeks after treatment start. Response is defined as a reduction of 35% or more on the Y-BOCS and a CGI-I score of 1 or 2. Remission is defined as a Y-BOCS score of 12 or less and a CGI-S score of 1 or 2. Proportions will be compared using a two-sided two-proportions z-test.

Dropout rate

To explore whether the groups differ in terms of treatment completion, we will compare whether the proportion of patients that discontinue treatment prematurely differs between B4DT and gold standard CBT. A dropout will be defined as a patient in the B4DT arm that participates in less than 1.5 full days at the clinic, or a patient in the gold standard CBT arm that participates in less than 8 CBT sessions. Proportions will be compared using a two-sided two-proportions z-test.

Negative effects

To describe negative treatment effects, a two-sample t-test will be used to compare the total NEQ-scores at the primary endpoint (scores on the subscales will be presented in the supplement). The additional semi-structured questions about suicidal behaviors and thoughts, hospitalization, deterioration of psychiatric symptoms, and psychiatric care outside the study, will be reported in a frequency table.

Cost effectiveness

Health economic data will be collected using the self-rated Treatment Inventory of Costs in Psychiatric Patients (TIC-P) questionnaire [11]. The TIC-P records costs for the past month

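### The intention-to-treat sensitivity analysis is meant to address non-random missing data but names only a missing-at-random method, does not name the week 4 and 7 Y-BOCS scores, and has no tipping-point step

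*Combined protocol and SAP*

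**What the plan says.** The combined protocol and SAP (Statistical analysis, Primary outcome, Y-BOCS) bases the primary test on patients who received at least half of their treatment and completed the week-14 assessment, with no imputation. The ANCOVA adjusts for the pre-treatment score only. For sensitivity, "the same ANCOVA model will be used again but with an intention to treat approach", and "Missing data will then be estimated using maximum likelihood after which the models are refitted". The purpose is stated as: "The aim of these steps is to address the potential influence of non-random missing data in the primary per protocol analysis". No predictors are listed for this step.

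Under Secondary outcomes in the same part, imputation is used only when more than 10% of data are missing, and then consists of "maximum likelihood imputations based on demographics and the scores from the pre-treatment assessment". The reason given is that data are not collected continuously during treatment. Measurements and Table 2 nevertheless schedule blinded Y-BOCS and CGI ratings at weeks 4 and 7 in both arms.

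The other checks, on dropout rates (Dropout rate) and on travel distance and broken blinding (Limitations), do not deal with missing week-14 scores. No delta-adjusted, tipping-point or pattern-mixture analysis appears.

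**The concern.** The aim and the method do not match. A missing-at-random method cannot show what happens if patients who disappear do worse than their recorded data predict.

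Three things follow from the text.

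- **No information from lost patients.** If the likelihood uses only arm and baseline, as the wording implies, it reproduces the complete-case result.
- **Useful data left unnamed.** The two interim ratings are the best available predictors of a missing week-14 score.
- **Possible understated standard error.** Estimating missing values and then refitting reads as single imputation, which treats filled-in values as observed.

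This is the only planned re-estimate of the primary effect that includes patients outside the per-protocol set. Unequal loss is plausible: the Introduction says of weekly CBT, "This extensive time-frame requires significant effort and persistence from patients and increases the risk of dropout". If the estimate falls near the margin, the plan has no way to show whether lost patients could overturn non-inferiority.

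**Working it through.** Differences are B4DT minus CBT, so positive values mean B4DT is worse.

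**Inputs from the plan.** Margin 4; one-sided 2.5%; 60 per arm; pre-treatment mean 22.6 (SD 3.78); CBT post-treatment mean 12.9 (SD 4.07); true difference 0; 10% missing (Sample size calculation).

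**Assumptions.** Pre-post correlation 0.3; week 7 to week 14 correlation 0.7; log-odds of loss 1.5 per SD of the driving score; loss rates other than 10%.

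**1. The plan's own figure.** With 54 evaluable per arm and no covariate gain, SE = 4.07 × √(2/54) = 0.783, and power = Φ(4/0.783 − 1.96) = 99.9%. This agrees with the stated power above 95%, which is not in dispute.

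**2. Baseline-only likelihood.** A patient with no week-14 score carries no information on the regression of that score on arm and baseline. Values filled in from the fitted line have zero residual, so refitting returns the same coefficients. In simulation the two estimates agreed to about 1e-13.

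**3. Bias** (4,000 simulated trials per scenario, true difference 0, Monte Carlo error about 0.01):

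| Loss driven by | B4DT / CBT loss | Baseline only | With weeks 4 and 7 |
|---|---|---|---|
| week-7 score | 15% / 5% | −0.27 | about 0 |
| week-7 score | 5% / 15% | +0.27 | about 0 |
| week-7 score | 10% / 10% | about 0 | about 0 |
| unseen week-14 score | 15% / 5% | −0.41 | −0.25 |

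In the week-7 rows the interim scores remove the bias by construction. The last row shows they are not enough when loss depends on the unseen outcome. With a pre-post correlation of 0.5, the first two baseline-only figures become −0.18 and +0.17. Non-inferiority held in at least 99.8% of these trials, with mean upper bounds of 1.0 to 1.9.

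**4. Covariance by arm.** At week 4, "B4DT-group will have received their full treatment dose at the point of assessment while the gold standard CBT-group will have received only about 25" per cent, so interim scores may predict week 14 differently in the two arms. Assume the week 7 to week 14 correlation is 0.8 in B4DT and 0.5 in CBT:

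| B4DT / CBT loss | Baseline only | Weeks 4 and 7, common slopes | Weeks 4 and 7, by arm |
|---|---|---|---|
| 15% / 5% | −0.39 | −0.15 | +0.01 |
| 5% / 15% | +0.09 | −0.16 | 0.00 |
| 10% / 10% | −0.14 | −0.14 | +0.01 |

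Equal loss is therefore not always harmless, and a common covariance is not enough.

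**5. Tipping shift.** With a share p missing, the worsening of missing B4DT scores that brings the upper bound to 4 is approximately (4 − d − 1.98 × SE)/p, where d is the estimate and SE = 4.07 × √(1 − 0.3²) × √(2/(60(1 − p))).

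| p | SE | d = 0 | d = 2 |
|---|---|---|---|
| 10% | 0.747 | (4 − 1.479)/0.10 = 25 | 5.2 |
| 15% | 0.769 | (4 − 1.523)/0.15 = 17 | 3.2 |
| 20% | 0.793 | (4 − 1.570)/0.20 = 12 | 2.2 |

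For scale, the assumed mean improvement on CBT is 22.6 − 12.9 = 9.7 points. The shifts at d = 0 all exceed it; those at d = 2 are well below it.

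**6. Impute-then-refit read literally.** The ratio of reported to true SE is about √[((n_obs − 3)/117) × (1 − p)], where n_obs = 120(1 − p). At 10% this is √[(105/117) × (54/60)] = 0.90; at 15% and 20% it is 0.85 and 0.80. The one-sided error at a true difference of 4, Φ(−1.98 × ratio), is 3.8%, 4.7% and 5.7%. Simulation (20,000 trials per rate) gave ratios of 0.90, 0.84 and 0.79 and errors of 3.9%, 4.9% and 6.0%, against 2.4 to 2.5% without imputation.

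**7. Response at week 14** (Y-BOCS part only; 67% respond under these inputs). Baseline-only imputation shifts the difference by +2.4 percentage points at 15%/5% loss and −2.4 if reversed. With weeks 4 and 7 the shift is about 0.

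**The case against.** - **Non-random may be meant loosely**, as selective rather than strictly dependent on unseen values, and the intention-to-treat step does restore under-treated patients who were assessed at week 14. Both points stand. But on the loose reading, likelihood helps with missing scores only if predictors of loss are in the model, and none beyond baseline is named.
- **The public scripts may specify predictors and a proper variance.** They were not available here. The baseline-only reading of the primary step is inferred, and the single-imputation reading is one of two; direct likelihood would not understate the SE. This limits the finding to the plan text, which settles neither.
- **The bias is small and depends on assumptions.** It is 0.27/4 = 7% of the margin, or 0.27/0.747 = 0.36 SE, with a threefold imbalance in loss. It falls to −0.11 with log-odds of 0.5, or −0.12 with 12%/8% loss. If CBT loses more, as the Introduction suggests, the main scenario favours CBT and is conservative. If the true difference is 0, an estimate of 2 or more has probability of about 0.4%. All of this stands, and it limits severity.
- **Secondary analyses are exploratory**, and the self-rated symptom scales and the NEQ have no week 4 or 7 values. A shift of 2.4 percentage points is small beside a confidence half-width of about 18. This also stands: the criticism of secondary imputation applies only to outcomes built on Y-BOCS or CGI.

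**Conclusion.** The concern holds for the plan as written. The sensitivity analysis cannot do what it is said to do: it names one missing-at-random method, names no interim predictors, and no missing-not-at-random analysis is planned. The wording also permits an analysis with an understated standard error.

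The primary per-protocol test is unaffected. In the scenarios simulated, the baseline-only bias ranged from −0.41 to +0.27 points, and with a true difference near 0 the conclusion would rarely change. The gap matters if the estimate approaches 2 points or loss approaches 20%, when missing-score shifts of roughly 2 to 5 points would bring the upper bound to the margin. Loss rates other than the planned 10%, the correlations and the loss mechanism are assumptions. The change should be made, but it is not critical to the primary test.

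**What to change.** 1. Replace the intention-to-treat missing-data step with a direct-likelihood repeated-measures model of blinded Y-BOCS at weeks 4, 7 and 14 in all randomized patients. Include baseline, arm, visit, baseline × visit and arm × visit, with an unstructured covariance estimated separately by arm. Report the week-14 B4DT minus CBT contrast with its 95% CI. Multiple imputation by arm from weeks 0, 4 and 7, with proper variance, is an alternative; the plan already uses multiple imputation for the economic analysis.
2. Add a delta-adjusted tipping-point analysis, because the model in item 1 also assumes missing at random. Shift missing week-14 scores in 1-point steps, separately by arm, and report the shifts at which the upper bound reaches 4. Only this step tests non-random loss.
3. For response and remission at week 14, use multiple imputation that includes the week 4 and 7 Y-BOCS and CGI ratings.
4. State the method and predictors in the SAP text and align the published scripts with it.

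The cost is wording and code. All the data are already scheduled, with no extra patients or visits. The by-arm covariance has 12 parameters: 6 more than a pooled unstructured matrix and 11 more than the ANCOVA's single residual variance. The sensitivity interval will be wider than impute-then-refit would give.
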